3.2.2.2 Follow-up Phase

- Sustained Negativity Rate at weeks 8, 12, 16, 20, and 24.
- Proportion of ALT or AST above baseline, at Grade 1 and above at weeks 8, 12, 16, 20, and 24.
- Incidence of SAEs.
- Change from baseline and 24-week signs and symptoms identified as part of the "Post Ebola Syndrome" from PREVAIL III data on completed review of symptoms and physical exam, depression, and post-traumatic stress disorder screening.

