13.3 Sample Size Justification

Preliminary data from PREVAIL III was used to estimate the rates of detectable virus in semen of survivors. Among 134 men who contributed at least two semen samples, we analyzed the last two semen samples per person. One hundred men had undetectable CT at both time points, 13 (10%) were detectable at both time points, and 21 (16%) had mixed detectability (detectable/undetectable or undetectable/detectable). Based on these estimates, 26% of male survivors may be eligible for the study.

We use this data to estimate the proportion of men who might be eligible for the study as well as the "success" rate among placebos. The enrollment is limited by the number of available subjects with detectable Ebola virus in semen at screening. Based on semen testing in PREVAIL III, approximately 26% of male survivors will have detectable seminal Ebola viral RNA when tested longitudinally during the first 1-2 year window. This percentage may decrease with time.

Based on the power calculations below, complete data on 50 men (25/arm) should be adequate to find a difference under many assumptions. However, as the power calculations do not take into account missing data, nor is it clear what type of heterogeneity or treatment effect might be more realistic, the study will attempt to enroll at least 60 people (30/group), with a target of at least 20 participants with two screening samples with a detectable CT or at least 30 participants have an Ebola NP or GP CT value using the Cepheid of <39. If the total sample size of 60 is enrolled without 20 people with two detectable samples, or at least 30 participants with an Ebola NP or GP CT value using the Cepheid of <39 we will continue to enroll until one of these criteria is met up to a total of 120 people if possible.

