13.3.1 Power Calculations

The table below lists the simulated power to find a significant difference in treatment-phase ANR and follow-up ANR for various true rates of ANR in the placebo and GS-5734 arms. With 50 people (25/arm), we will have reasonable power (>80%) to find a difference in both the treatment-phase ANR and the follow-up ANR if the effect of treatment is to cut the probability of a detectable sample by 50% for each person at each time, starting at day 3. If the effect of treatment is instead that 40% of people experience sterilization starting on day 3, such that their probability of a detectable sample drops to 0 (except for false positives), and the rest of the people are unaffected, then the power varies depending on the amount of heterogeneity in the probabilities.

ANR p-value based on t-test on proportion negative at 6 (day 3 to day 28) or 5 (week 8 to week 24) visits. All power estimates based on 1,000 simulations, 1% false positive rate, and 5% false negative rate, alpha=.05, no adjustments for multiple comparisons.

Ν	P _i =P(detectable person i) Control group	Treatment Effect	Power d3- d28 ANR	Power w8- w24 ANR
50	pi=.5	.5	.96	.98
	p _i ~Beta(10,10)	(multiplicative on probability)	.93	.97
	$p_i \sim U(0,1)$	starting d5	.95	.98
	$p_i = \begin{cases} . \ 1 \ with \ 50\% \ chance \\ . \ 9 \ with \ 50\% \ chance \end{cases}$.97	.99
50	p _i =.5	.4	.77	.84
	pi~Beta(10,10)	(Probability sterilize)	.85	.89
	$p_i {\sim} U(0,\!1)$	starting d5	.16	.23

Table 11	. Power	for	endpoints	under	varying	assumptions.
----------	---------	-----	-----------	-------	---------	--------------

		Р	REVAIL IV
		,	Version 10.0
		1	3 May 2019
$p_i = \begin{cases} . \ 1 \ with \ 50\% \ chance \\ . \ 9 \ with \ 50\% \ chance \end{cases}$.52	.67	

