This study could generate considerable missing data as a consequence of the dose de-escalation plan and unsuccessful donations at individual visits. If there is substantial missingness (more than just a few) then the previous analysis will need to adjust for differences in the number of observations among participants as the proportions from different participants will have different variances under the null hypothesis. This will be accomplished by replacing the 2 sample t-test with a t-test of the regression coefficient associated with an indicator variable for group membership (i.e. active or placebo) from a weighted linear regression analysis with weights given by the number of study visits for which a participant successfully made a donation (these weights are a consequence of inverse relationship between the variance of a binomial proportion and the number of trials).

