13.4.1 Secondary Endpoints

Secondary analyses or safety and tolerability endpoints will include tabulation of grade 2 and higher laboratory values, including but not limited to ALT and AST, and adverse events by treatment arm.

Secondary analyses will examine the effect of defining a positive CT value to be any reading of 40 or lower, as well as the main analysis based on a per-protocol definition of treatment arm. Other secondary analyses will include per protocol analyses, Generalized Estimating Equations models for the serial binary endpoints of detectability, exact tests of proportions for binary endpoints such as Sustained Negativity Rate (no detectable Ebola RNA at any included time point), and censored regression models to compare CT trajectories will also be performed.

In the event that the study-wide dose is reduced to 75 mg, a secondary analysis will be restricted to people on both arms enrolled after the dose reduction.

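### Sustained Negativity has no rule for missed semen samples, so missed donations can raise the rate in either arm and bias the comparison towards the arm that misses more

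*Combined protocol and SAP*

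**What the plan says.** Sustained Negativity is a follow-up-phase secondary objective (section 2.2.2) and a listed secondary endpoint: "Sustained Negativity Rate at weeks 8, 12, 16, 20, and 24" (section 3.2.2.2). Its only definition is in the analysis text of section 13.4.1, which calls for "exact tests of proportions for binary endpoints such as Sustained Negativity Rate (no detectable Ebola RNA at any included time point"). No section defines an included time point, sets a minimum number of samples, or says how a missed donation counts.

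Missing samples are foreseen. Section 13.4 states: "This study could generate considerable missing data as a consequence of the dose de-escalation plan and unsuccessful donations at individual visits". The remedy is that "then the previous analysis will need to adjust for differences in the number of observations among participants". It is a regression weighted by the number of successful donations, and it replaces the t-test on ANR. Nothing equivalent is given for Sustained Negativity. Section 13.3 adds that "the power calculations do not take into account missing data".

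The ANR test in section 13.4 is stratified by number of positive screening samples and by country, matching the randomisation. Section 13.4.1 mentions no stratification for the exact tests.

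**The concern.** ANR and Sustained Negativity react differently to lost samples. If samples are lost at random, a man's expected ANR does not change; it only becomes less precise, and weighting deals with that. Sustained Negativity is an all-negative score. A sample that was never given cannot show a detection, so every lost sample raises the chance that the man counts as cleared. Read literally, one negative and four missed donations score the same as five negatives, and a man with no samples also meets the wording.

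Two things are at stake. The reported rate overstates clearance in any arm with missed donations, even when both arms miss equally. If one arm misses more, the comparison is shifted in its favour with no drug effect at all.

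**Working it through.** **Inputs.** Five scheduled samples (section 3.2.2.2). Control-group detection probabilities p from Table 11: 0.5 for every man; U(0,1); and 0.1 or 0.9 with equal chance. Assay error: "1% false positive rate, and 5% false negative rate, alpha=.05, no adjustments for multiple comparisons" (section 13.3.1). Size: "the study will attempt to enroll at least 60 people (30/group"), extendable to 120 in total (section 13.3). The documents give no missing rate, so the rates below are assumptions, with samples missing completely at random. The plan states no rate or power for Sustained Negativity (Table 11 concerns ANR), so there is no figure to reproduce.

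**Step 1: chance of no detection in k samples, U(0,1), no assay error.** The integral of (1−p)^k over 0 to 1 is 1/(k+1). This gives 1/6 = 17% for five samples, 1/4 = 25% for three, 1/3 = 33% for two and 1/2 = 50% for one.

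**Step 2: with assay error.** The probability that a sample reads positive is d = 0.95p + 0.01(1−p), and the chance of no detection is E[(1−d)^k].

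| Samples given | p = 0.5 | U(0,1) | 0.1 or 0.9 |
|---|---|---|---|
| 5 | 0.038 | 0.167 | 0.289 |
| 3 | 0.141 | 0.255 | 0.361 |
| 2 | 0.270 | 0.344 | 0.412 |
| 1 | 0.520 | 0.520 | 0.520 |

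**Step 3: rate in an arm with per-visit missing probability m, observed samples only, no drug effect.** The rate is E[{m + (1−m)(1−d)}^5]. At p = 0.5, 1−d = 0.52:
- m = 0.30: (0.30 + 0.70 × 0.52)^5 = 0.664^5 = 12.9%
- m = 0.10: (0.10 + 0.90 × 0.52)^5 = 0.568^5 = 5.9%

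At 30% v 10% missing, U(0,1) gives 24.2% v 18.7%, and 0.1/0.9 gives 34.8% v 30.6%.

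**Step 4: men selected as in this trial.** Eligibility needs at least one of two screening samples positive, so each p is weighted by 1−(1−d)². Under U(0,1) this gives 6.7% with complete data, 12.9% v 8.2% at 30% v 10% missing, and 12.9% in both arms at 30% v 30%.

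**Step 5: false significance.** Two-sided Fisher test, no drug effect, unselected distributions, 6,000 simulated trials per setting. Entries are the share significant in favour of the arm with more missing data; the nominal limit is 2.5% per side. With nothing missing the simulated rate was 0% to 1.5% per side.

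| Missing | Men per arm | p = 0.5 | U(0,1) | 0.1 or 0.9 |
|---|---|---|---|---|
| 30% v 10% | 30 | 4.2% | 4.0% | 3.2% |
| 40% v 10% | 30 | 16.1% | 8.0% | 4.7% |
| 40% v 10% | 60 | 44.8% | 17.3% | 8.4% |

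At 20% v 5% with 30 per arm the range is 1.4% to 2.3%, which is inside the limit.

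**Step 6: other simple rules.**
- *Missing scored as not negative.* The rate becomes (1−m)^5 times the complete-data rate. The multipliers are 0.7^5 = 0.168 and 0.9^5 = 0.590, so the Step 4 setting gives 1.1% v 4.0%. The bias reverses.
- *Only men with all five samples.* This is unbiased here, but keeps only 17% of an arm with 30% missing.

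**Step 7: stratifying the test.** Selected U(0,1), 30 per arm, detection cut by 50%: an exact conditional test on the strata raised power from about 22% to 28%. A second run with complete data, using only the screening-sample stratum, gave 23% to 26%. Under no effect with 30% missing in both arms, the stratified test's two-sided error was 2.0%. At 30% v 10% missing, false significance for the arm with more missing was 2.9% unstratified and 4.2% stratified, so stratification does not cure the missing-data problem.

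**The case against.** The strongest reply has four parts.

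- *The plan does not state a biased rule.* A reader might infer that it tells the analyst to count one negative and four misses as sustained negative. It does not; it leaves the included time points undefined. This stands: the fault is an open rule, of which the literal reading is one outcome.
- *The drug arm need not be the one that misses more.* A reader might infer this from the link to dose de-escalation in section 13.4, and from the Phase 1 multiple-dose study, where graded ALT elevations occurred in 8 of 16 people on drug and 1 of 8 on placebo (section 1.2.3.2). But de-escalation acts in the five dosing days and the endpoint is read at weeks 8 to 24. Placebo recipients have matching adjustments (section 5.5.3), and men who stop study agent continue in follow-up for safety (section 11.5.1.1, which is silent on semen). The other cause named, unsuccessful donation, has no evident link to arm. This stands: the direction is not established.
- *The size rests on assumed rates.* It does. At modest imbalance the error stays within the nominal limit, and with equal missingness there is no bias between arms. Both reported rates are still inflated then.
- *The endpoint is secondary.* Both primary analyses use ANR, which has a missing-data provision, and section 13.4.1 also plans Generalized Estimating Equations on visit-level results. These limit the consequence, but neither repairs the Sustained Negativity rate or its test.

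**Conclusion.** The point holds as a gap in the specification of a secondary endpoint. Without a rule for missed donations, the natural reading inflates the rate in any arm with missed samples and tilts the comparison towards the arm that misses more. In the illustration closest to the trial's own selection, 30% missing in both arms roughly doubles the rate (6.7% to 12.9%), and 30% v 10% produces a gap of 12.9 − 8.2 = 4.7 percentage points from a drug that does nothing. These figures rest on U(0,1) shedding, the plan's assay error rates, missingness unrelated to viral status, and missing rates that are assumed.

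The documents do not support the stronger claims that the result will favour GS-5734 or that primary ANR is affected in this way. Nor is scoring missed samples as not negative a safe conservative default: it penalises whichever arm misses more, so if placebo misses more it favours the drug. The missing stratification is a lesser point, with a modest gain in power at stake.

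**What to change.** Amend section 13.4.1 before unblinding:

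1. Define the endpoint over all five scheduled visits: weeks 8, 12, 16, 20 and 24.
2. Score a man with any detection as not sustained negative, whatever else is missing.
3. For men with no detection but missed samples, use multiple imputation from arm, stratum and observed results as the main analysis.
4. Add two bounding sensitivity analyses: missed samples counted as positive, and observed samples only. These bracket each arm's rate; crossing them between arms brackets the difference.
5. Report the number of samples per man by arm.
6. Replace the unstratified exact test with an exact conditional or within-stratum permutation test on number of positive screening samples and country, as section 13.4 already does for ANR. State how the imputed data sets enter the test, for example by repeating the imputation within each permutation.

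The cost is analysis-plan wording and a little more analysis work. The main result will rest on a missing-at-random assumption, which the bounding analyses put in view. No visit, sample or sample-size change is needed.

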13.5 Operational Futility

Since not all male survivors are interested in enrolling in PREVAIL III, any confirmed male survivor interested in participating in this study will be considered for screening/enrollment.

14 Ethics/Protection of Human Subjects

14.1 Informed Consent Process

Informed consent is a process where information is presented to enable persons to voluntarily decide whether or not to participate as a research subject. It is an ongoing conversation between the human research subject and the researchers which begins before consent is given and continues until the end of the subject's involvement in the research. Discussions about the research will provide essential information about the study and include: purpose, duration, experimental procedures, alternatives, risks, and benefits. Subjects will be given the opportunity to ask questions and have them answered.

The subjects will sign the informed consent document prior to undergoing any research procedures. The subjects may withdraw consent at any time throughout the course of the trial. A copy of the informed consent document will be given to the subjects for their records. The researcher will document the signing of the consent form in the subject's record. The rights and welfare of the subjects will be protected by emphasizing to them that the quality of their medical care will not be adversely affected if they decline to participate in this study.

14.2 Subject Confidentiality

All records will be kept confidential to the extent provided by federal, state, and local law. The study monitors and other authorized representatives of the sponsor may inspect all documents and records required to be maintained by the investigator, including but not limited to, medical records. Records will be kept locked and all computer entry and networking programs will be done with coded numbers only. Clinical information will not be released without written permission of the subject, except as necessary for monitoring by the IRBs, the FDA, NIAID, OHRP, the pharmaceutical supporter, or the sponsor's designee.

PREVAIL IV Version 10.0 13 May 2019

15 Data Handling and Record Keeping

15.1 Data Capture and Management

Study data will be maintained on CRFs and collected directly from subjects during study visits and telephone calls, or will be abstracted from subjects' CRFs from PREVAIL III when available. Source documents include all recordings of observations or notations of clinical activities and all reports and records necessary to confirm the data abstracted for this study. Data entry onto CRFs will be performed by authorized individuals. The investigator is responsible for assuring that the data collected are complete, accurate, and recorded in a timely manner.

15.2 Record Retention

The investigator is responsible for retaining all essential documents listed in the ICH GCP guidelines. Study records will be retained for a minimum of 5 to 7 years and in compliance with institutional, IRB, state, and USG federal, Liberian and Guinean medical records retention requirements, whichever is longest. All stored records will be kept confidential to the extent required by USG, Liberian, and Guinean federal, state, and local law.

Should the investigator wish to assign the study records to another party and/or move them to another location, the investigator will provide written notification of such intent to OCRPRO/NIAID with the name of the person who will accept responsibility for the transferred records and/or their new location. Destruction or relocation of research records will not proceed without written permission from OCRPRO/NIAID.

PREVAIL IV Version 10.0 13 May 2019

Evaluations/	Pre-	Screening/ Week 0 (within 21		y 1 ^f ision)	Day	Day	Day Day 3 4		Day 8	Day 11	Day 16	Day Day 16 24		Wk. 8 ^g	Wk. 12	Wk. 16	Wk. 20	Wk. 24 ^g (+5 days)
Procedures	Screen ^a	days prior to Day 1)	Pre- dose	Post- dose	2	3			(+1)	(+1)	(±2)	(±2)	28 ^r (+3)	(±14 days)	(±14 days)	(±14 days)	(±14 days)	End of Study
Pre-Screening Informed Consent	Х																	
Informed consent		Х																
Demographics (participant and contacts)		Х																
Targeted Physical exam/signs & symptoms			Х	X ^d	X ^d	X ^d	X ^d	X ^d	X ^d	X ^d	X ^d	X ^d	X ^d	X ^d	X ^d	X ^d	X ^d	
Vital signs		Х	Xc	Xc	Xc	Xc	Xc	Xc	X ^d	X ^d	Х	X ^d	X ^d	Х	Х	Х	Х	Х
Completed Medical Exam & ROS/ medication history		Х																Х
Medical and EVD history ^a		Х																
Depression Questionnaire		Х																Х
PTSD Questionnaire ^a		Х																Х
Stigma and Discrimination Questionnaire ^a		х																
Randomize subject		Х																
Infusion				Х	Х	Х	Х	Х										

Appendix B: Schedule of Procedures/Evaluations

PREVAIL IV Version 10.0 13 May 2019

Assessment for Adverse events				Х	Х	Х	Х	Х	Х	Х	Х	Х	Х	Х	Х	Х	Х	Х
Review of concomitant meds		Х	Х		Х	Х	Х	Х	Х	Х	Х	Х	Х	Х	Х	Х	Х	Х
Participant satisfaction survey													Х					Х
Blood Samples																		
Chemistries, total and direct bilirubin, AST/ALT, and lipids		Х	Х		Xj	Xj	Xj	Xj	Х	Х	Х	Х	Х	Х	Х	Х	Х	Х
CBC with diff		Х	Х		Xj	Xj	Xj	Xj	Х	Х	Х	Х	Х	Х	Х	Х	Х	Х
Prothrombin time (PT), aPTT, INR, and D-dimer		Х	Х		Xj	Xj	Xj	Xj	Х	Х	Х	X	Х	Х	Х	Х	Х	Х
Leftover serum and plasma storage		Х	X ⁿ		Xj	Xj	Xj	Xj	Х	Х	Х	Х	Х	Х	Х	Х	Х	Х
GS-5734 PK and metabolites - plasma ^o				\mathbf{X}^{h}			Xj	X ^h										
PBMCs for intracellular concentrations - PK°								Xi										
eGFR		Х																
Ebola antibody levels		Х																Х
Semen Samples Ebola PCR with CT for NP & GP	Xb	X ^m					X ^k		Х	Х	Х	Х	Х	Х	Х	Х	Х	Х
Ophthalmologic Exam	Xe																	X^1
HIV and Syphilis Test		X ^p																

^a Participants in Guinea can sign a pre-screening informed consent form for semen collection and testing. Procedures conducted under PREVAIL III will be accepted for PREVAIL IV pre-screening.

^b Positive PCR for NP or GP using the GeneXpert assay at pre-screening in at least one of two or more semen samples within 42 days of randomization.

^c On infusion days, vital signs will be obtained within 30 minutes prior to start of infusion and 30 minutes and 60 minutes after infusion completes.

^d Performed only if needed to evaluate new symptoms/complaints.

^e Baseline ophthalmologic exam to be conducted within 4 months of enrollment in PREVAIL IV. The baseline ophthalmologic exam can be extracted from PREVAIL III data if done within 4 months prior to enrollment in PREVAIL IV. Ophthalmologic exams must be repeated if conducted > 4 months prior to enrollment in PREVAIL IV or if they were not previously done.

^f Beginning & end of Treatment phase with DSMB evaluation planned for end of treatment phase.

^g Beginning & end of Follow up phase.

^h Draw immediately after infusion if possible and not later than 5 minutes after infusion.

ⁱ Draw within 1 hour after infusion, but may be drawn with the PK plasma sample drawn within 5 minutes after infusion.

^j Pre-infusion sample.

^k Day 4 semen samples can +1 e.g. on days 4 or 5 but only one semen sample is needed during infusion.

¹End of study ophthalmologic exam to be done at 24 weeks +/- 6 weeks

^m An additional semen sample will be collected during the screening period if the participant has only had one sample with Ebola viral RNA detected or already had two previous semen tests with at least one positive detection of Ebola virus RNA and the last semen sample was collected greater than 21 days prior to enrollment. Note that the results of this sample **do not** affect subject eligibility. A participant with one previous semen sample with positive Ebola virus RNA detected within the -42-day window can provide the second required sample for randomization during the -21 day screening period, if they are able. The results of this sample will be used to stratify the participant and should be done on days -21 to -3.

ⁿA portion of excess serum will be used for future serologic testing for hepatitis B and hepatitis C.

^o When site facility conditions do not allow processing of PK samples, sample should not be collected.

^p In Guinea and in Liberia for participants not co-enrolled in PREVAIL III.

Appendix C. eGFR Calculation

A normal serum creatinine does not necessarily reflect a normal Glomerular Filtration Rate (GFR). Serum creatinine alone is not a sensitive indicator for mild to moderate kidney injury. Estimate glomerular filtration rate (GFR) can be estimated e(GFR) from measured serum creatinine. Normal estimated GFR (eGFR) has been calculated from population level studies (NHANES III) in the US and have been extensively validated for Caucasians and African Americans and will be used in this study because similar data is not available for Liberia. The eGFR will be estimated using the Chronic Kidney Disease Epidemiology Collaboration formula (CKD-EPI) for PREVAIL IV. The West African male population is muscular and lean with low BMI, in a tropical climate without climate control, and a cultural tendency not to drink water. The CKD-EPI has not been validated in the African non-American population. eGFR varies by age; the table below will be used to determine normal age eGFR to determine eligibility.

eGFR Method: The CKD-EPI equation for African American males is:

Ref: Levey AS, Stevens LA, et al. A New Equation to Estimate Glomerular Filtration Rate. Ann Intern Med. 2009; 150:604-612.

The equation does not require weight or height variables because the results are reported normalized to 1.73 m^2 body surface area, which is an accepted average adult surface area.

The table below shows population estimates for mean (average) estimated glomerular filtration rate (eGFR) by age. These means, derived from the NHANES III survey of over 10,000 individuals in the US, demonstrate that eGFR varies across age groups and that kidney function tends to decline with age.

Age (Years)	Mean eGFR*
18 ^a -29	116 mL/min/1.73 m ²
30-39	107 mL/min/1.73 m ²
40-49	99 mL/min/1.73 m ²
50-59	93 mL/min/1.73 m ²
60-69	85 mL/min/1.73 m ²
70+	75 mL/min/1.73 m ²

Reference Table for Population Mean eGFRs From NHANES III

^a Lower age range adjusted from 20years to 18 years of age

